8.6 CD3 T-Lymphocyte Quantification (Optional)

8.6.1 Description of Studies and Assay

Peripheral blood samples will be collected from consenting patients to aid in identifying biomarkers of response through flow cytometric analysis of CD3+ T-cells. Changes in T cell number will be described and exploratory analysis will be conducted to assess their correlation with clinical features including occurrence of infections and response. Samples will be analyzed locally at the treating institution.

8.6.2 Sampling Schedule (See [Appendix X](#))

Blood samples will be collected from consenting patients at the following time points:

- Cycle 1: Day 1 pre-infusion, and Days 8, 15, 22, and 29 (prior to the end of infusion)
- Subsequent cycles, Day 1: Pre-infusion

8.6.3 Sample Collection and Handling Instructions

Blood samples (2 – 3 ml) will be collected in EDTA tubes (or institutional standard) and analyzed locally via flow cytometry according to institutional standards. **NOTE:** Patients \leq 23 kg should only have 2 ml of blood drawn per sample. Blood samples will be collected at a site distant from the infusion for T cell quantification. Samples cannot be drawn from the 2nd lumen of a multi-lumen catheter through which drug is being administered. Record the exact time that the sample is drawn along with the exact time that infusion begins on Day 1 of each cycle.

The date and time of sample collection will be recorded on the CD3 T-Lymphocyte Quantification Study Form ([Appendix X](#)) and uploaded into RAVE. Quantification results will be collected in RAVE per the guidance in the CRF packet.

8.7 Cytokine Production Measurement (Optional)

8.7.1 Description of Studies and Assay

Peripheral blood samples will be collected from consenting patients to improve mechanistic understanding of potential therapeutic responses and adverse effects with flotetuzumab therapy. Samples will be analyzed through a qualified ELISA assay by MacroGenics Pharmaceuticals.

8.7.2 Sampling Schedule (See [Appendix XI](#))

Blood samples will be collected from consenting patients at the following time points:

- Cycle 1, Day 1: pre-infusion
- Cycle 1, Day 8

Additionally, if patients experience IRR/CRS, blood samples will be collected from consenting patients at the following time points:

THIS PROTOCOL IS FOR RESEARCH PURPOSES ONLY, SEE PAGE 1 FOR USAGE POLICY

- At the time of IRR/CRS
- At the time of IRR/CRS resolution

8.7.3 Sample Collection and Handling Instructions

Blood samples (2 – 3 ml) will be collected in SST tubes at a site distant from the infusion for cytokine production measurement evaluation. **NOTE:** Patients ≤ 23 kg should only have 2 ml of blood drawn per sample.

8.7.4 Sample Processing

1. Collect blood into a 2 – 3 mL SST tube.
2. Allow blood to clot for at least 60 minutes at room temperature.
3. Separate serum within 60 – 90 minutes of collection.
4. Centrifuge for 10 minutes at room temperature at 1100 – 1300 x g.
5. Transfer serum equally into two 2 mL orange capped cryovials (primary and back up).
6. Immediately freeze at -60°C to -80°C .

8.7.5 Sample Labeling

Each tube must be labeled with the patient's study registration number, the study I.D., and the date and time the sample was drawn. Data should be recorded on the Cytokine Analysis Study Form ([Appendix XI](#)), which must accompany the sample(s).

Additionally, MacroGenics has standard naming conventions for samples. Sites should use the below labeling conventions for lab samples:

Pre MGD006 CK
Day 8 CK
Start IRR/CRS CK
End IRR/CRS CK
UNS CK (use this for unscheduled)

8.7.6 Sample Shipping Instructions

Store samples at -70°C until shipment. Ship on dry ice to Washington University once all samples have been collected for each patient. Prior to sample shipment, please email [REDACTED] to alert her of the sample shipment. Ship to the following address:

[REDACTED]
[REDACTED]
[REDACTED]
[REDACTED]
[REDACTED]

NOTE: Primary and back-up aliquots from the same time point should NOT be sent in the same shipment.

8.8 Profiling of the Tumor Microenvironment (Optional)

THIS PROTOCOL IS FOR RESEARCH PURPOSES ONLY, SEE PAGE 1 FOR USAGE POLICY

8.8.1 Description of Studies and Assay

Bone marrow aspirate and biopsy will be collected from consenting patients to aid in identifying biomarkers of response through gene expression profiling, protein analysis, and patient-derived xenograft modeling. Studies will be performed via the [name] Lab at the Children's Hospital of Philadelphia.

8.8.2 Sampling Schedule

Bone marrow aspirate and biopsy will be collected from consenting patients at the following time points:

- Prior to Cycle 1

While the preferred specimen is bone marrow, if bone marrow samples cannot be obtained, peripheral blood may be sent in for patients who have an absolute blast count $\geq 1,000/\mu\text{L}$

In addition to the bone marrow aspirate or blood sample, 1 paraffin-embedded tissue block will be collected. If a block of tissue is unavailable, 10 unstained slides and 2 H&E stained slides may be collected instead.

8.8.3 Sample Collection and Handling Instructions

Bone marrow samples (10 – 15 mL) will be collected in green top sodium heparin tubes at the time of bone marrow evaluation.

If peripheral blood is obtained, 20 – 30 mL of blood will be collected in green top sodium heparin tubes. **NOTE:** Patients ≤ 23 kg should only have 20 mL of blood drawn per sample.

8.8.4 Sample Processing

Store samples at 4°C until shipment.

8.8.5 Sample Labeling

Each tube must be labeled with the patient's study registration number, the study I.D., and the date and time the sample was drawn. Data should be recorded on the Tumor Microenvironment Study Form ([Appendix XII](#)), which must accompany the sample(s).

8.8.6 Sample Shipping Instructions

For questions regarding sample collection, processing, and shipping, please email [REDACTED]

Samples may be shipped at room temperature or with an ice pack. If samples are to be shipped with an ice pack, the collection tubes are to be wrapped in paper towels or other insulation to minimize tube freezing and direct contact with the ice pack.

Prior to sample shipment, please email [REDACTED] [REDACTED]

Ship samples to the following address:

THIS PROTOCOL IS FOR RESEARCH PURPOSES ONLY, SEE PAGE 1 FOR USAGE POLICY

[figure not shown]
Following sample shipment, send another email to the addresses listed above with the Fed-Ex tracking number and copy the PEPN1812 Research Coordinator on the email.

9.0 AGENT INFORMATION

9.1

9.1.1

9.1.2

9.1.3

9.1.4

THIS PROTOCOL IS FOR RESEARCH PURPOSES ONLY, SEE PAGE 1 FOR USAGE POLICY

9.1.4.2

For more information, contact the Office of the Vice President for Research and the Office of the Vice President for Student Affairs.

A black and white test pattern consisting of a series of horizontal bars of varying widths. A single vertical bar is positioned in the center of the pattern. The bars are arranged in a repeating sequence of widths across the frame.

A thick black horizontal bar located at the bottom of the page, spanning most of the width of the content area.

A black and white graphic consisting of a grid of horizontal lines. The top line is thick and black. Below it are several thinner horizontal lines. The fourth line from the top contains five smaller black rectangles of varying widths, positioned in the middle of the line. The other lines are completely blank.

THIS PROTOCOL IS FOR RESEARCH PURPOSES ONLY, SEE PAGE 1 FOR USAGE POLICY

9.1.5

9.1.6

THIS PROTOCOL IS FOR RESEARCH PURPOSES ONLY, SEE PAGE 1 FOR USAGE POLICY

A series of horizontal black bars of varying lengths and positions, likely representing data points or markers on a timeline. The bars are arranged in several distinct groups. The first group consists of a long bar at the top, a shorter bar below it, and a very short bar near the center. The second group is located in the middle-left area, containing a long bar and a shorter bar. The third group is in the middle-right area, containing a long bar and a shorter bar. The fourth group is at the bottom, containing a long bar and a shorter bar. The fifth group is at the very bottom, containing a long bar and a shorter bar. The bars are solid black and have no internal structure.

[figure not shown]
A program funded by the National Cancer Institute of the National Institutes of Health

9.1.6.5

[figure not shown]
THIS PROTOCOL IS FOR RESEARCH PURPOSES ONLY, SEE PAGE 1 FOR USAGE POLICY

THIS PROTOCOL IS FOR RESEARCH PURPOSES ONLY, SEE PAGE 1 FOR USAGE POLICY

THIS PROTOCOL IS FOR RESEARCH PURPOSES ONLY, SEE PAGE 1 FOR USAGE POLICY

[figure not shown]

THIS PROTOCOL IS FOR RESEARCH PURPOSES ONLY, SEE PAGE 1 FOR USAGE POLICY

[figure not shown]
9.1.7

9.1.8

THIS PROTOCOL IS FOR RESEARCH PURPOSES ONLY, SEE PAGE 1 FOR USAGE POLICY

THIS PROTOCOL IS FOR RESEARCH PURPOSES ONLY, SEE PAGE 1 FOR USAGE POLICY

[figure not shown]

THIS PROTOCOL IS FOR RESEARCH PURPOSES ONLY, SEE PAGE 1 FOR USAGE POLICY

A horizontal bar chart with a single data series represented by black bars. The bars are of varying lengths, indicating the magnitude of the data points. The chart is set against a white background with a light gray grid.

9.1.10

THIS PROTOCOL IS FOR RESEARCH PURPOSES ONLY, SEE PAGE 1 FOR USAGE POLICY

9.2 **Cytarabine** (07/13/15)

(Cytosine arabinoside, Ara-C, Cytosar®) NSC# 63878

9.2.1 Source and Pharmacology

Cytarabine appears to act through the inhibition of DNA polymerase. A limited, but significant, incorporation of cytarabine into both DNA and RNA has also been reported. It exhibits cell phase specificity, primarily killing cells undergoing DNA synthesis (S-phase) and under certain conditions blocking the progression of cells from the G1 phase to the S-phase. Cytarabine is metabolized by deoxycytidine kinase and other nucleotide kinases to the nucleotide triphosphate (Ara-CTP), an effective inhibitor of DNA polymerase. Ara-CTP is inactivated by a pyrimidine nucleoside deaminase, which converts it to the nontoxic uracil derivative (Ara-U). It appears that the balance of kinase and deaminase levels may be an important factor in determining sensitivity or resistance of the cell to cytarabine. It has an initial distributive phase $t_{1/2}$ of about 10 minutes, with a secondary elimination phase $t_{1/2}$ of about 1 to 3 hours. Peak levels after intramuscular or subcutaneous administration of cytarabine occur about 20 to 60 minutes after injection and are lower than IV administration. Intrathecally administered doses are metabolized and eliminated more slowly with a $t_{1/2}$ of about 2 hours.

9.2.2 Toxicity: (Intrathecal)

	Common Happens to 21-100 children out of every 100	Occasional Happens to 5-20 children out of every 100	Rare Happens to < 5 children out of every 100
Immediate: Within 1-2 days of receiving drug	Nausea, vomiting, fever, headache	Arachnoiditis	Rash, somnolence, meningismus, convulsions, paresis
Prompt: Within 2-3 weeks, prior to the next course			Myelosuppression, ataxia
Delayed: Any time later during therapy, excluding the above condition			Necrotizing leukoencephalopathy, paraplegia, blindness (in combination with XRT & systemic therapy)

9.2.3 Formulation

Cytarabine for Injection is available as a preservative free solution 20 mg/mL (5 mL, 50 mL per vial) or 100 mg/mL (20 mL vial). Hydrochloric acid and/or sodium hydroxide may be added to adjust the pH. Store intact vials of solution at 15°-30°C (59°-86°F). Cytarabine solutions should be protected from light.

THIS PROTOCOL IS FOR RESEARCH PURPOSES ONLY, SEE PAGE 1 FOR USAGE POLICY

9.2.4 Guidelines for Administration

See Treatment and Dose Modification sections of the protocol.

Intrathecal:

For intrathecal administration, dilute with 5-10 mL (or volume per institutional practice) preservative free 0.9% sodium chloride injection, lactated Ringer's injection, Elliot's B solution. The volume of CSF removed should be equal to at least $\frac{1}{2}$ the volume delivered.

Patient Age (years)	Recommended volume	10% CSF volume	CSF Volume *
1 – 1.99	5 – 10 mL	5 mL	50 \pm 10 mL (babies)
2 – 2.99	5 – 10 mL	8 mL	80 \pm 20 mL (younger children)
3 – 8.99	5 – 10 mL	10 mL	100 \pm 20 mL (older children)
9 or greater	5 – 10 mL	13 mL	130 \pm 30 mL (adults)

*Rieselbach, R.E. et.al. Subarachnoid distribution of drugs after lumbar injection; *N Engl J Med.* 1962 Dec 20; 267:1273-8

Of Note: Larger volumes approximating at least 10% of the CSF volume, isovolumetric delivery, with the patient remaining prone after the procedure may facilitate drug distribution. These procedures have not been validated in clinical trials. They are allowed but not mandated for patients on COG studies.

Intrathecal cytarabine mixed in NS, lactated Ringer's injection, or Elliot's B solution is stable for 24 hours at 25°C but contains no preservative and should be administered as soon as possible after preparation.

9.2.5 Supplier

Commercially available from various manufacturers. See package insert for further information.

9.3 Useful Links and Contacts

- CTEP Forms, Templates, Documents:
<http://ctep.cancer.gov/forms/>
- NCI CTEP Investigator Registration:
[contact]
- CTEP Identity and Access Management (IAM) account:
<https://ctepcore.nci.nih.gov/iam/>
- CTEP Associate Registration and IAM account help:
[contact]
- IB Coordinator:
[contact]

10.0 CRITERIA FOR REMOVAL FROM PROTOCOL THERAPY AND OFF STUDY CRITERIA**10.1 Criteria for Removal from Protocol Therapy**

- a) Clinical (including physical examination or serum tumor markers) or radiographic

THIS PROTOCOL IS FOR RESEARCH PURPOSES ONLY, SEE PAGE 1 FOR USAGE POLICY

evidence of progressive disease (See [Section 12](#)).

- b) Have not achieved at least a PR following 2 successive treatment cycles.
- c) Adverse Events requiring removal from protocol therapy (See [Section 13](#)).
- d) Development of a DLT following 1 dose reduction.
- e) An infusion stop or delay of more than 2 weeks due to AE or more than 2 discontinuations per cycle due to AE (does not apply for prolongation of the scheduled treatment free period of a cycle).
- f) Refusal of protocol therapy by patient/parent/guardian
- g) Non-compliance that in the opinion of the investigator does not allow for ongoing participation.
- h) Completion of 6 cycles of therapy.
- i) Physician determines it is not in the patient's best interest.
- j) Repeated eligibility laboratory studies (CBC with differential, bilirubin, ALT (SGPT) or serum creatinine) are outside the parameters required for eligibility prior to the start of flotetuzumab (See [Section 8.1](#)).
- k) Study is terminated by Sponsor.
- l) Pregnancy

Patients who are removed from protocol therapy during Cycle 1 should continue to have the required observations in [Section 8.1](#) until the originally planned end of the cycle or until all adverse events have resolved per [Section 13.4.4](#), whichever happens LATER. The only exception is with documentation of the patient's withdrawal of consent. Patients who are removed from protocol therapy in subsequent cycles should have the necessary observations to ensure adequate clinical care.

Patients who are off protocol therapy are to be followed until they meet the criteria for Off Study (see below). Ongoing adverse events, or adverse events that emerge after the patient is removed from protocol therapy, but within 30 days of the last dose of investigational agent, must be followed and reported via RAVE and CTEP-AERS (if applicable). Follow-up data will be required unless consent is withdrawn.

10.2 Off Study Criteria

- a) Thirty days after the last dose of the investigational agent.
- b) The patient does not receive protocol treatment after study enrollment.
- c) Death
- d) Lost to follow-up
- e) Withdrawal of consent for any required observations or data submission.
- f) Enrollment onto another COG therapeutic (anti-cancer) study

11.0 STATISTICAL AND ETHICAL CONSIDERATIONS

11.1 Sample Size and Study Duration

This is a Phase 1 study involving a dose escalation cohort using a rolling six design with a primary aim of identification of safe and tolerable dosing of the CD123 x CD3 DART, flotetuzumab, in children between < 21 years of age with AML in second or greater relapse, refractory AML after two or more chemotherapy cycles, or first relapse after primary chemotherapy-refractory disease. Prior hematopoietic stem cell transplantation (HSCT) is permitted.

If DL1 is safe and tolerable based on standard immunotherapy DLT assessments, an additional cohort of patients will dose-escalate to flotetuzumab at 700 nanograms/kg/day (DL2). If fewer than 2 DLTs occur at DL2, this will be considered the RP2D. If there are ≥ 2 DLTs at DL2, DL1 will be considered the MTD of flotetuzumab monotherapy. If flotetuzumab monotherapy at DL1 is not tolerable, dose de-escalation will occur to 300 nanograms/kg/day (DL-1). If DL-1 is deemed tolerable, this dosing will be the MTD. Further dose de-escalation beyond DL-1 will not be permitted and will limit further exploration of flotetuzumab in this patient population. Bone marrow evaluation will be performed with blood count recovery from Cycle 1 therapy as an exploratory measurement of response. Patients with at least stable disease after Cycle 1 may continue to Cycle 2. Patients with at least a PR following Cycle 2 may receive subsequent cycles of flotetuzumab for a total of up to 6 cycles.

A minimum of 4 evaluable patients and a maximum of 18 will be required for determination of the MTD/RP2D. Once the MTD or RP2D has been defined, up to 6 additional patients with AML in second or greater relapse, refractory AML after two or more chemotherapy cycles, first relapse after primary chemotherapy-refractory disease, or first relapse after HSCT without restrictions on heme evaluability may be enrolled to acquire PK data in a representative number of young patients (i.e. patients < 12 years old). Review of the enrollment rate into previous COG new agent studies indicates that 1-2 patients per month are available, which will permit completion of the study within 27 months. A maximum of 27 patients is anticipated allowing for three dose levels, PK expansion, and 10% attrition. In the unlikely event that each dose level is expanded to 12 patients, an absolute maximum of 47 patients may be required allowing for 10% inevaluability, and this would be completed within 47 months.

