5.5.1 Non-hematological dose-limiting toxicity

5.5.1.1 Any Grade 3 or greater non-hematological toxicity at least possibly attributable to protocol therapy with the specific exclusion of:

- Alopecia
- Grade 3 fatigue, anorexia, nausea, vomiting, and diarrhea not requiring hospitalization, tube-feeding, or use of TPN.
- Grade 3 liver enzyme elevation, including ALT/AST, occurring after flotetuzumab administration that returns to Grade ≤ 1 or baseline within 7 days from the start of therapy. Note: For the purposes of this study the ULN for ALT is defined as 45 U/L.
- Grade 3 or 4 fever, febrile neutropenia, or infection
- Grade 3 or 4 isolated electrolyte abnormalities that resolve with or without intervention to \leq Grade 2 within 72 hours. Electrolyte supplementation is encouraged.
- Grade 3 or 4 tumor lysis syndrome that resolves within 7 days without end-organ damage.
- Grade 3 rash that resolves (with or without supportive care) to \leq

THIS PROTOCOL IS FOR RESEARCH PURPOSES ONLY, SEE PAGE 1 FOR USAGE POLICY

Grade 2 within 7 days

- Grade 3 mucositis that resolves (with or without supportive care) to \leq Grade 2 within 7 days
- Early intervention with TPN or enteral tube feeding for anorexia, nausea not attributable to protocol therapy, or concern for poor nutritional status clearly and incontrovertibly not attributable to protocol therapy will not be considered a DLT
- Grade 3 or greater pain due to leukemia, mucositis, typhlitis, infection, or obvious injury
- Grade 3 IRR (including CRS) resolving to \leq Grade 2 within 72 hours. CRS will be defined by ASBMT consensus grading³⁶
- Cases of Hy's law ($> 3x$ ULN of ALT/AST along with $> 2x$ ULN in total bilirubin without evidence of cholestasis) will be considered a DLT if no other reason can be found to explain the observed injury (e.g. leukemia, infection, another drug, etc.).

5.5.1.2 Non-hematological toxicity that causes a delay of ≥ 14 days between treatment cycles.

5.5.1.3 Note: Allergic reactions that necessitate discontinuation of study drug will not be considered a dose-limiting toxicity.

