11.2.2 Maximum Tolerated Dose

- The MTD will be the maximum dose at which fewer than one-third of patients experience DLT (See [Section 5.5](#) during Cycle 1 of therapy).
- If two or more of a cohort of up to six patients experience DLT at a given dose level, then the MTD has been exceeded and dose escalation will be stopped. If review of the DLTs suggests that they would potentially be acceptable (e.g., because of rapid reversibility, different classes of Adverse Effects) or are potentially attributable to disease rather than therapy, then expansion of the cohort to 12 patients to better assess tolerability of this dose level will be considered assuming the following conditions are met:
 - One of the DLTs does not appear to be dose-related
 - The Adverse Effects are readily reversible

THIS PROTOCOL IS FOR RESEARCH PURPOSES ONLY, SEE PAGE 1 FOR USAGE POLICY

- The study chair, DVL statistician, DVL committee chair or vice chair, IND sponsor, and CTEP all agree that expansion of the cohort is acceptable

If fewer than 1/3 of patients in the expanded cohort experience dose-limiting toxicities, the dose escalation can proceed.

- The DLTs observed in the pharmacokinetic (PK) expansion cohort will be counted towards the total number of DLTs observed at the MTD during the dose escalation portion of the study. If $\geq 1/3$ of the cohort of patients at the MTD (during the dose escalation plus the PK expansion) experience DLT then the MTD will be exceeded.

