11.3 Dose Escalation and Determination of MTD

The rolling six phase 1 trial design will be used for the conduct of this study.³⁵ Two to six patients can be concurrently enrolled onto a dose level, dependent upon (1) the number of patients enrolled at the current dose level, (2) the number of patients who have experienced DLT at the current dose level, and (3) the number of patients entered but with tolerability data pending at the current dose level. However, enrollment will be staggered so that no more than 1 patient initiates enrollment every 7 days for dose levels greater than DL1. Accrual is suspended when a cohort of six has enrolled or when the study endpoints have been met.

Dose level assignment is based on the number of participants currently enrolled in the cohort, the number of DLTs observed, and the number of participants at risk for developing a DLT (i.e., participants enrolled but who are not yet assessable for toxicity). For example, when three participants are enrolled onto a dose cohort, if toxicity data is available for all three when the fourth participant entered and there are no DLTs, the dose is escalated and the fourth participant is enrolled to the subsequent dose level. If data is not yet available for one or more of the first three participants and no DLT has been observed, or if one DLT has been observed, the new participant is entered at the same dose level. Lastly, if two or more DLTs have been observed, the dose level is de-escalated. This process is repeated for participants five and six. In place of suspending accrual after every three participants, accrual is only suspended when a cohort of six is filled. When participants are inevaluable for toxicity, they are replaced with the next available participant if escalation or de-escalation rules have not been fulfilled at the time the next available participant is enrolled onto the study.

The following table provides the decision rules for enrolling a patient at (i) the current dose level (ii) at an escalated dose level, (iii) at a de-escalated dose level, or whether the study is suspended to accrual:

# Pts Enrolled	# Pts with DLT	# Pts without DLT	# Pts with Data Pending	Decision
2	0 or 1	0, 1 or 2	0, 1 or 2	Same dose level

THIS PROTOCOL IS FOR RESEARCH PURPOSES ONLY, SEE PAGE 1 FOR USAGE POLICY

2	2	0	0	De-escalate*
3	0	0, 1 or 2	1, 2 or 3	Same dose level
3	1	0, 1 or 2	0, 1 or 2	Same dose level
3	0	3	0	Escalate**
3	≥ 2	0 or 1	0 or 1	De-escalate*

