4	0	0, 1, 2 or 3	1, 2, 3 or 4	Same dose level
4	1	0, 1, 2 or 3	0, 1, 2 or 3	Same dose level
4	0	4	0	Escalate**
4	≥ 2	0, 1 or 2	0, 1 or 2	De-escalate*
5	0	0, 1, 2, 3 or 4	1, 2, 3, 4 or 5	Same dose level
5	1	0, 1, 2, 3 or 4	0, 1, 2, 3 or 4	Same dose level
5	0	5	0	Escalate**
5	≥ 2	0, 1, 2 or 3	0, 1, 2 or 3	De-escalate*
6	0	0, 1, 2, 3, or 4	2, 3, 4, 5 or 6	Suspend
6	1	0, 1, 2, 3 or 4	0, 1, 2, 3 or 4	Suspend
6	0 or 1	5 or 6	0 or 1	Escalate**
6	≥ 2	0, 1, 2, 3 or 4	0, 1, 2, 3 or 4	De-escalate*

* If six patients already entered at next lower dose level, the MTD has been defined.

** If final dose level has been reached, the recommended dose has been reached.

If two or more of a cohort of up to six patients experience DLT at a given dose level, then the MTD has been exceeded and dose escalation will be stopped (see [Section 11.2.2](#) for exception to rule).

In addition to determination of the MTD, a descriptive summary of all toxicities will be reported.

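### Sections 2.5, 5.1 and 11.1 name DL1 the MTD after two DLTs at DL2 without condition, while the 11.3 table returns to DL1 when fewer than six are entered there

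*Combined protocol and SAP*

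**What the plan says.** **The prose.** Sections 2.5, 5.1 and 11.1 each give one consequence of two or more DLTs at DL2. In 11.1 it reads "DL1 will be considered the MTD of flotetuzumab monotherapy". None of the three mentions how many patients DL1 has treated.

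**The table and its text.** Section 11.3 allows DL1 to be left early: with three assessed and no DLT, "the dose is escalated and the fourth participant is enrolled to the subsequent dose level". The table gives the same action for 0/4 and 0/5. In the other direction, "Lastly, if two or more DLTs have been observed, the dose level is de-escalated". Each de-escalation row carries a footnote: "If six patients already entered at next lower dose level, the MTD has been defined".

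**The definition and its exceptions.** Section 11.2.2 defines the MTD by a DLT proportion below one-third and gives no minimum number. After two DLTs in a cohort of up to six, it adds that under stated conditions "then expansion of the cohort to 12 patients to better assess tolerability of this dose level will be considered". DLTs in the PK expansion "will be counted towards the total number of DLTs observed at the MTD during the dose escalation portion of the study".

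**The sample size.** Section 11.1 states: "A minimum of 4 evaluable patients and a maximum of 18 will be required for determination of the MTD/RP2D". It then gives 27 enrolled (three dose levels, PK expansion, 10% attrition) and an absolute maximum of 47 (every level expanded to 12).

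**The concern.** The two rules agree only if six patients were entered at DL1 before escalation. If three, four or five were entered and DL2 then shows two DLTs, the prose stops and names DL1, while the table assigns the next patient to DL1.

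This is the decision rule for primary aim 1.1.2. Under the prose, DL1 could be named after five patients in all: 0/3 at DL1 and 2/2 at DL2. Two study teams following the same protocol could act differently at that moment, and the choice between the rules would be made after the DL2 data were known.

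**Working it through.** **1. Reproduce the stated sample sizes.** All reachable paths were counted before PK expansion and without 12-patient cohorts. A tolerated level closes at 3 to 6 patients and a failed level at 2 to 6. Under the table, a reopened DL1 is taken to be filled to six.

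- Table rule, minimum: 2 at DL1 + 2 at DL-1 = 4. Maximum: 6 + 6 + 6 = 18 (DL1 left early, DL2 fails, DL1 reopened and fails, then DL-1).
- Prose rule, minimum: 4. Maximum: 6 + 6 = 12, because no path uses three levels.

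Enrolled maximum = (evaluable + 6 PK patients) / 0.9:

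| | Table rule | Prose rule | Section 11.1 |
|---|---|---|---|
| Evaluable maximum | 18 | 12 | 18 |
| Enrolled, six per level | 24/0.9 = 26.7, so 27 | 18/0.9 = 20 | 27 |
| Enrolled, 12 per level | (36+6)/0.9 = 46.7, so 47 | (24+6)/0.9 = 33.3, so 34 | 47 |

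**2. Evidence behind the named MTD.** Exact two-sided 95% upper limits on the DLT rate; with no events the limit is 1 − 0.025^(1/n).

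- Prose: 0/3 gives 71%, 0/4 gives 60%, 0/5 gives 52%.
- Table, with DL1 filled to six: 0/6 gives 46%. The table also accepts 1/6, which gives 64%.

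**3. How often the conflict arises.** A rolling-six trial was simulated from the 11.3 table: DL1 then DL2, 20,000 trials per setting, Poisson arrivals, uniform DLT times, 7-day stagger at DL2. Accrual of 1 to 2 patients a month comes from 11.1. The windows are the 29-day cycle and the 42-day haematological limit in 5.5.2.

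DLT rates are assumptions. The 13% at DL1 is grade 3 or higher IRR/CRS in 4/31 adults; the 33% at DL2 is 3/9 adults at 700 nanograms/kg/day (both Section 2.3.1). Both are loose guides, because 5.5.1 excludes "Grade 3 IRR (including CRS) resolving to" grade 2 or less within 72 hours, and the adult grade 3 or higher events lasted a median of 2.5 days.

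Chance of two or more DLTs at DL2 with fewer than six at DL1, at 1 / 1.5 / 2 patients a month and 13% at DL1:

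| DL2 rate | 29-day window | 42-day window |
|---|---|---|
| 15% | 9 / 7 / 5% | 7 / 4 / 2% |
| 33% | 28 / 21 / 14% | 21 / 12 / 7% |
| 50% | 39 / 29 / 19% | 29 / 17 / 9% |

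Other DL1 rates widen this. DL1 at 5% with DL2 at 50% gives 54% (1 a month, 29 days); DL1 at 35% with DL2 at 15% gives 0.8% (2 a month, 42 days).

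**4. How often the named dose would change.** Filling DL1 to six overturns it in 0.1% to 0.9% of trials in the 13%/33% case, and in at most about 3% with DL1 at 10% to 40% and DL2 at 33% to 50%.

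**5. What the PK expansion would catch.** At a true DL1 rate of one-third, chance of overturning DL1:

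| Start | Six PK patients (at least one-third of all with DLT) | Filling DL1 to six (two or more DLTs) |
|---|---|---|
| 0/3 | P(Bin(6,1/3) ≥ 3) = 32% | P(Bin(3,1/3) ≥ 2) = 26% |
| 0/4 | P(Bin(6,1/3) ≥ 4) = 10% | (1/3)² = 11% |
| 0/5 | P(Bin(6,1/3) ≥ 4) = 10% | 0% |

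After 0/3, no PK patients or only one cannot overturn DL1, since 1/4 is below one-third.

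**The case against.** The prose can fairly be read as shorthand. Sections 2.5 and 11.1 introduce it as a summary of a rolling six design, 11.3 describes its table as the source of the enrolment decisions, and the prose plainly omits other detail, such as the 12-patient exception. The 11.1 maxima match the table, although 18 may simply be three levels of six. So the intended rule is largely recoverable. What remains is that no clause gives 11.3 precedence and the unconditional sentence appears three times, once in the statistical section itself.

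The table is also less firm than it first looks. A reader might infer that it expressly forbids naming DL1 until six are entered. The footnote says if, not only if; the stricter sense comes from reading it together with the de-escalation action. Nor does the table guarantee six. Once DL1 is reopened, 0/4 or 0/5 with no data pending falls on an escalate row, back to DL2. A minimum of eight patients (six at DL1, two at DL2) before DL1 is named therefore needs a rule against re-escalation that is not written.

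Finally, 11.2.2 counts DLTs in the PK expansion, and from 0/3 a full expansion catches a toxic DL1 slightly more often than filling the cohort would. That protection is real but partial: the expansion is optional, of up to six patients.

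**Conclusion.** The conflict stands as an internal inconsistency in the decision rule for a primary aim, at the low end of should-fix. It bites only when three to five patients are at DL1 as DL2 fails. The figure of about 2% to 40% of trials rests on the assumed 13% at DL1 and on DL2 rates of 15% to 50%; it is not a bound over all plausible DL1 rates.

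A reader might go further and infer that the prose would lead the trial to a wrong dose. The calculations do not support that: over the settings run, filling DL1 to six seldom changes the dose named. At 0/5 a sixth patient cannot bring DL1 to two DLTs, so there only the number treated differs. The gain in precision is also modest if the sixth-patient result is 1/6. The defect is that two written rules prescribe different actions, and that one of them lets the MTD rest on three patients.

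**What to change.** Reconcile 2.5, 5.1 and 11.1 with 11.2.2 and 11.3 before any DL2 data are seen, so that one rule governs.

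- **Simplest route.** Make the three prose sentences subject to 11.2.2 and 11.3, for example: if two or more DLTs occur at DL2, DL1 is named the MTD once six patients have been entered there and fewer than one-third had DLT; otherwise enrolment continues under 11.3. Keep the footnote's count of patients entered, or flag openly any change to evaluable patients, which is a different count under 11.2.1. The figures 18, 27 and 47 then stand.
- **With it.** State how the table applies when DL1 is reopened, including whether the escalate rows still operate. That choice is the sponsor's.
- **Alternative.** If the sponsor keeps the prose rule, remove the footnote condition and restate the maxima as 12 evaluable, and 20 and 34 enrolled.

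The cost is wording in three sections and one table note. Under the table's rule, up to three more patients are treated at DL1, and up to six more at DL-1 if the reopened DL1 fails. All fall within the stated 18.
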